## 3 Statistical analysis

---

### 3.1 Statistical principles

#### 3.1.1 Level of statistical significance

The study includes two formal interim analysis after approximately one third and two thirds of patients have completed their 90-day follow-up, using the Haybittle-Peto stopping rule (3 standard-deviations) for efficacy. To account for these two interim analyses, the significance threshold will be set at 4.82% for the final analysis. In case the trial is stopped early, the significance threshold will be adjusted accordingly, to account for the amount of 'alpha' spent.

Final analysis of the primary outcome, including sensitivity analyses, will all be conducted using a two-sided significance level of 4.82%.

For the 7 secondary clinical outcomes ([1] death or dependency at 7 days, and the following at 90 days: [2] death or major disability, [3] death, [4] disability, [5] HRQoL, [6] Duration of hospitalisation and [7] residence ), the family-wise error rate will be controlled by applying a sequential Holm-Sidak correction. Briefly, the approach consists of ordering all p values from smallest to largest, and then comparing them to an adjusted level of significance calculated as  $1-(1-0.05)^{1/C}$ , where C indicates the number of comparisons that remain. In the case of seven 7 secondary outcomes, the smallest p value would be compared to  $1-(1-0.05)^{1/7}$ , the second p value to  $1-(1-0.05)^{1/6}$ , and so on, with the last one being compared to  $1-(1-0.05)$  (i.e. 0.05). The sequential testing procedure stops as soon as a p value fails to reach the corrected significance level. This will apply only to the primary analysis of the secondary outcomes (i.e. not to the adjusted models). For HRQoL, it will only apply to the analysis of the overall score. For ICH outcomes, the Heidelberg Bleeding Classification (HBC) criteria will be considered the primary measure with other definitions considered supportive. No multiplicity adjustment will be applied to the two imaging outcomes (infarct and oedema size) which are considered intermediary mechanistic outcomes.

### 3.1.2 *Software*

Analyses will be conducted primarily using SAS Enterprise Guide (version 9.3 or above) and R (version 4.0.0 or above).

## 3.2 Data sets analysed

**Intention-to-treat (ITT) population:** The ITT population will consist of all patients randomised regardless of whether they received the allocated intervention. This will be used as the basis to assess both efficacy and safety.

**Efficacy analysis set:** The main analysis set will consist of all patients in the ITT population with a non-missing primary outcome (i.e. those who are known to have died or with mRS cores at 90 days). In case of missing data leading to exclusion from the ITT population, sensitivity analyses will be performed (see Section 3.7.4).

**Per-protocol (PP) analysis set:** The PP set will consist of patients from the efficacy analysis who did not have a relevant protocol violation, defined as any of: age <18 years; final diagnosis not AIS; SBP <140 mmHg (inclusion criteria BP level); EVT undertaken >24 hours; EVT did not achieve reperfusion (eTICI score <2b); and failure to obtain a blind assessment of the 90-day outcome. The per-protocol set will be applied as a sensitivity analysis.

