6.3 Inclusion / exclusion criteria

*To be eligible for inclusion for this study, patients **ARE** to satisfy all of the following criteria:*

- 1) Adult (age ≥ 18 years)
- 2) Clinical diagnosis of AIS with LVO (anterior or posterior circulation) on imaging
- 3) To receive MT < 24 hours after AIS onset according to local guidelines
- 4) Successful recanalization (TICI score $\geq 2b$)
- 5) Sustained systolic BP ≥ 140 mmHg (defined as 2 successive readings < 10 minutes) within 3 hours after recanalization
- 6) Provide informed consent (or by appropriate proxy, according to local requirements)

Patients will NOT be eligible if there is one or more of the following:

- 1) Considered unlikely to benefit from therapy (e.g. advanced dementia, major pre-stroke disability, high likelihood of death within 24 hours post-MT on the basis of clinical assessment), as judged by the responsible treating clinician
- 2) Other medical illness that interferes with outcome assessments and follow-up (e.g. known significant pre-stroke disability (mRS scores 3-5), advance cancer and renal failure)
- 3) Definite indication/contraindication to either immediate intensive BP lowering (SBP <120 mmHg) or a higher BP target (SBP 140-180 mmHg)
- 4) Specific contraindications to any of the BP agents to be used (eg, patients who are hypersensitive (allergic) to any of the ingredients)
- 5) Patients with aortic isthmus stenosis and arteriovenous shunt (exception: patients with haemodynamically inactive dialysis shunt)
- 6) Women who are lactating
- 7) Currently participating in another trial which may interfere with outcome assessments

All AIS patients screened for the study that are not included, as well as recruited patients, must be recorded on a screening/enrolment log. This information is to be uploaded to the CCC database. The decision of eligibility is on the attending clinician's interpretation and consideration for the balance of potential benefits and risks pertaining to the level of BP control on each particular patient.

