#### 2.2.1 *Inclusion Criteria*

- Age ≥18 years
- Diagnosis of AIS with LVO confirmed by brain imaging
- To receive EVT <24 hours after the onset of symptoms, according to local guidelines
- Successful recanalisation (defined by expanded treatment in cerebral infarction [eTICI] score of ≥2b) after EVT (See Appendix 1)
- Sustained SBP ≥140 mmHg (defined as 2 successive readings <10 mins apart) within 3 hours after recanalisation
- Provide written informed consent (or from an approved surrogate).

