## Appendix 2: Proposed Tables and figures

### 4.1 Tables

**Table 1. Baseline characteristics**

	Intensive BP lowering (N = )	Guideline-recommended BP lowering (N = )	Total (N = )
Age (years)	xxx	xxx	xxx
Mean (SD)	xxx.x (xxx.x)	xxx.x (xxx.x)	xxx.x (xxx.x)
Median (Q1; Q3)	xxx (xxx; xxx)	xxx (xxx; xxx)	xxx (xxx; xxx)
min max	xxx to xxx	xxx to xxx	xxx to xxx
Sex	xxx	xxx	xxx
Male	xxx xx.x%	xxx xx.x%	xxx xx.x%
Female	xxx xx.x%	xxx xx.x%	xxx xx.x%
Ethnicity	xxx	xxx	xxx
Chinese	xxx xx.x%	xxx xx.x%	xxx xx.x%
Caucasian/European	xxx xx.x%	xxx xx.x%	xxx xx.x%
Other	xxx xx.x%	xxx xx.x%	xxx xx.x%
Systolic Blood Pressure (mmHg) on arrival	xxx	xxx	xxx
Mean (SD)	xxx.x (xxx.x)	xxx.x (xxx.x)	xxx.x (xxx.x)
Median (Q1; Q3)	xxx (xxx; xxx)	xxx (xxx; xxx)	xxx (xxx; xxx)
min max	xxx to xxx	xxx to xxx	xxx to xxx
Diastolic Blood Pressure (mmHg) on arrival	xxx	xxx	xxx
Mean (SD)	xxx.x (xxx.x)	xxx.x (xxx.x)	xxx.x (xxx.x)
Median (Q1; Q3)	xxx (xxx; xxx)	xxx (xxx; xxx)	xxx (xxx; xxx)
min max	xxx to xxx	xxx to xxx	xxx to xxx
Heart Rate (bpm)	xxx	xxx	xxx
Mean (SD)	xxx.x (xxx.x)	xxx.x (xxx.x)	xxx.x (xxx.x)
Median (Q1; Q3)	xxx (xxx; xxx)	xxx (xxx; xxx)	xxx (xxx; xxx)
min max	xxx to xxx	xxx to xxx	xxx to xxx
Blood Glucose (mmol/L)	xxx	xxx	xxx
Mean (SD)	xxx.x (xxx.x)	xxx.x (xxx.x)	xxx.x (xxx.x)

	Intensive BP lowering (N = )	Guideline-recommended BP lowering (N = )	Total (N = )
Median (Q1; Q3)	xxx (xxx; xxx)	xxx (xxx; xxx)	xxx (xxx; xxx)
min max	xxx to xxx	xxx to xxx	xxx to xxx
Pre-stroke modified Rankin scale	xxx	xxx	xxx
0 - no symptoms	xxx xx.x%	xxx xx.x%	xxx xx.x%
1 - no significant disability (with symptoms)	xxx xx.x%	xxx xx.x%	xxx xx.x%
2 - slight disability (but independent in daily activities)	xxx xx.x%	xxx xx.x%	xxx xx.x%
3 - moderate disability (requiring some help from another person for daily activities)	xxx xx.x%	xxx xx.x%	xxx xx.x%
4 - moderate severe disability (requiring regular help from another person)	xxx xx.x%	xxx xx.x%	xxx xx.x%
5 - severe disability (bed bound, totally dependent)	xxx xx.x%	xxx xx.x%	xxx xx.x%
NIHSS Score on arrival	xxx	xxx	xxx
Mean (SD)	xxx.x (xxx.x)	xxx.x (xxx.x)	xxx.x (xxx.x)
Median (Q1; Q3)	xxx (xxx; xxx)	xxx (xxx; xxx)	xxx (xxx; xxx)
min max	xxx to xxx	xxx to xxx	xxx to xxx
GCS Score on arrival	xxx	xxx	xxx
Mean (SD)	xxx.x (xxx.x)	xxx.x (xxx.x)	xxx.x (xxx.x)
Median (Q1; Q3)	xxx (xxx; xxx)	xxx (xxx; xxx)	xxx (xxx; xxx)
min max	xxx to xxx	xxx to xxx	xxx to xxx

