**Table 17. Protocol violations and deviations**

Cause	Intensive BP lowering (N = )	Standard BP lowering (N = )
Eligibility violations	N=XXX	N=XXX
Age <18 years	nnn xx%	nnn xx%
Performed EVT ≥24 hours	nnn xx%	nnn xx%
Failed recanalisation (TICI <2b)	nnn xx%	nnn xx%
Not sustained SBP ≥140 mmHg within 3h after recanalisation		
Non-compliance with intervention	N=XXX	N=XXX
Reason 1	nnn xx%	nnn xx%
Reason 2	nnn xx%	nnn xx%
Etc.	nnn xx%	nnn xx%
Primary outcome	N=XXX	N=XXX
Non-blinded outcome assessment	nnn xx%	nnn xx%
Refused in-person or telephone assessment	nnn xx%	nnn xx%
Lost to follow-up	nnn xx%	nnn xx%
Etc.	nnn xx%	nnn xx%

*Programming notes:*

[figure not shown]
- *Reasons for non-compliance and missing outcome will be defined while blinded.*

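### The per-protocol set in SAP 3.2 applies only some of the eligibility criteria, and it conflicts with SAP 2.2.1 and Table 17 on the 24-hour limit and the qualifying blood pressure rule

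*SAP*

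**What the plan says.** SAP 3.2 builds the per-protocol set from the efficacy analysis set. It keeps patients "who did not have a relevant protocol violation, defined as any of: age <18 years; final diagnosis not AIS". The list continues with "SBP <140 mmHg (inclusion criteria BP level); EVT undertaken >24 hours; EVT did not achieve reperfusion (eTICI score <2b" and ends with "failure to obtain a blind assessment of the 90-day outcome". These six items are the whole definition.

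The eligibility rules are wider. On time, SAP 2.2.1 has "To receive EVT <24 hours after the onset of symptoms, according to local guidelines", and Protocol 6.3 gives the same limit. Both documents also require LVO on imaging and a qualifying SBP that is sustained over two readings within 3 hours of recanalisation. Among the exclusions, Protocol 6.3 gives "known significant pre-stroke disability (mRS scores 3-5" as an example of an illness that interferes with assessment, and SAP 2.2.2 does the same.

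SAP Table 17 has its own block of eligibility violations. It counts EVT at 24 hours or later, and it has a row for "Not sustained SBP ≥140 mmHg within 3h after recanalisation".

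On the role of the set, SAP 3.2 says "The per-protocol set will be applied as a sensitivity analysis". SAP 3.7.5 repeats the main and adjusted primary models in it, and SAP 3.8 repeats all secondary outcome analyses.

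**The concern.** A per-protocol analysis is usually read as the result in patients who met the entry criteria. Here the phrase that introduces the list closes it, so a programmer would code those six items and no others. On two rules, patients shown as eligibility violators in one SAP table would then be analysed as per protocol in the next. On two further criteria, LVO and pre-stroke disability, ineligible patients would stay in the set with no reason given.

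Two things are at stake. The first is interpretation: a patient who was already dependent before the stroke is unlikely to reach mRS 0-2 under either target, so keeping such patients pulls the dichotomised effect towards the null. The second is timing: if the mismatch is noticed only after unblinding, choosing which list governs becomes a post-hoc decision.

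**Working it through.** **Step 1: the rules side by side.**

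| Item | Eligibility (SAP 2.2, Protocol 6.3) | Per-protocol violation (SAP 3.2) | Violation in Table 17 |
|---|---|---|---|
| Age | 18 or over | under 18 | under 18 |
| AIS | required | final diagnosis not AIS | not listed |
| LVO | required | not listed | not listed |
| Time to EVT | <24 h | >24 h | ≥24 h |
| Reperfusion grade | 2b or better | below 2b | below 2b |
| Qualifying SBP | ≥140 mmHg, sustained, within 3 h | <140 mmHg (level only) | not sustained ≥140 mmHg within 3 h |
| Pre-stroke mRS 3-5 | excluded where known, as an example | not listed | not listed |

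The unblinded 90-day assessment appears in SAP 3.2 and, as an outcome deviation, in Table 17. It is not an eligibility item.

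**Step 2: test cases, each patient eligible in every other respect, with the rules taken literally.**

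| Patient | Eligible | Kept in per-protocol set | Table 17 violation |
|---|---|---|---|
| EVT at 23.9 h | yes | yes | no |
| EVT at exactly 24.0 h | no | yes | yes |
| EVT at 24.1 h | no | no | yes |
| SBP ≥140 mmHg first met at 4 h | no | yes | yes |
| No LVO | no | yes | no |
| Pre-stroke mRS 4 | no | yes | no |

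The 24.0 h and 4 h rows are direct conflicts between two parts of the SAP. The last two rows are omissions that SAP 3.2 and Table 17 share.

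**Step 3: are the data there?** Pre-stroke mRS is tabulated in Table 1 up to "5 - severe disability (bed bound, totally dependent" and is a covariate in SAP 3.7.2. Occlusion site is also in Table 1, and SAP 3.4 describes central adjudication of the site and degree of LVO. Table 17 already needs the 3-hour SBP rule to be programmed.

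**Step 4: size, for pre-stroke mRS 3-5.** The documents give no frequency. Assume that a fraction f of both arms has pre-stroke mRS 3-5 and always ends at mRS 3-6, and that the planning rates in SAP 2.5 (54% control, 47.52% intensive) hold for everyone else.

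- Planned OR for mRS 3-6: (0.4752/0.5248) / (0.54/0.46) = 0.9055/1.1739 = 0.771.
- Rate after mixing: p' = f + (1 − f)p.
- f = 1% (2257 × 0.01 ≈ 23 patients): control 0.5446, intensive 0.4804; OR = 0.9247/1.1959 = 0.773.
- f = 5% (2257 × 0.05 ≈ 113 patients): control 0.5630, intensive 0.5014; OR = 1.0058/1.2883 = 0.781.
- The absolute difference goes from 6.48 points to 6.48 × 0.95 = 6.16 points at f = 5%.

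So under an assumption that favours the concern, the OR moves by about 0.01.

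**The case against.** The case on the other side has several parts.

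- **The set is a chosen subset.** SAP 3.2 speaks of relevant violations, and it does apply age, AIS diagnosis, SBP level, a 24-hour limit and the reperfusion grade. This stands against any claim that eligibility is ignored. It does not explain why age is on the list while LVO is not.
- **Pre-stroke mRS 3-5 is not a free-standing numeric exclusion.** It is an example, limited to known disability, under a broader criterion, and Protocol 6.3 leaves eligibility to the attending clinician's interpretation. This stands: a grade learned only later is not clearly a violation. The rows for grades 3 to 5 in Table 1 show that the field exists, not that such patients are expected, since the table shells print full scales.
- **It is partly handled already.** The adjusted model includes pre-stroke mRS (SAP 3.7.2) and is repeated in the per-protocol set (SAP 3.7.5). This stands for that model, but the main model lacks the covariate.
- **The SBP wording may be shorthand for the full criterion,** and Protocol 6.6 places confirmation of eligibility within 3 hours after the procedure, which limits late qualifiers. This is possible, but the text names only the level while Table 17 spells out the window.
- **Few patients are involved.** Patients without LVO should be rare among those who had thrombectomy and reached grade 2b, and the 24-hour gap concerns only EVT at exactly 24 h. Both statements are fair.
- **A larger gap lies elsewhere:** the set has no criterion for compliance with the allocated BP target. That is a separate question and does not remove this one.

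**Conclusion.** The point holds as a limited inconsistency. Read literally, SAP 3.2 applies part of the eligibility criteria, conflicts with SAP 2.2.1 and Table 17 on two rules, and leaves out two criteria for which baseline data are planned. The consequence is confined to a sensitivity analysis and is probably small. The shift in OR from 0.771 to about 0.773-0.781 rests on an assumed 1-5% frequency, equal in both arms, with every such patient fixed at mRS 3-6. The exactly-24-h mismatch is a consistency correction with negligible numerical effect.

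A reader might go further in three ways, and the documents do not support any of them.

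- That the per-protocol result would not describe eligible patients. Five of the seven compared items are applied at least in part, and under the assumed range 95-99% of patients meet the pre-stroke disability criterion.
- That all the omissions set SAP 3.2 against Table 17. LVO and pre-stroke mRS are missing from both, so only the SBP rule and the 24-hour boundary are conflicts of that kind.
- That the primary result is affected. It uses the efficacy analysis set and all seven mRS levels, where patients with prior disability can still move among grades 3 to 6.

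**What to change.** Before unblinding, put one eligibility-violation list in both SAP 3.2 and Table 17:

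- age under 18;
- final diagnosis not AIS;
- no LVO on adjudicated imaging;
- known pre-stroke mRS 3-5, as recorded at baseline;
- EVT at 24 h or later;
- eTICI below 2b;
- no sustained SBP of at least 140 mmHg within 3 h of recanalisation.

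Keep the unblinded-assessment item in the per-protocol definition. State which vessels count as LVO, because neither document lists them and Table 1 includes sites such as M2, ACA, PCA and VA. If any criterion is left out on purpose, say why it is not considered relevant.

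The cost is a wording and programming change that uses data already planned for collection. It does not alter trial conduct or the primary analysis. The downside is a slightly smaller per-protocol set.

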## 3.3 Subject disposition

The flow of patients through the trial will be displayed in a CONSORT (Consolidated Standards of Reporting Trials) diagram. The report will include the following: the number of screened patients who met study inclusion criteria and the number of patients who were included; and reasons for exclusion of non-included patients.

### **3.4 Patient characteristics and baseline comparisons**

Description of the baseline characteristics will be presented by treatment group as outlined in Appendix 1 (Table 1). Discrete variables will be summarised by frequencies and percentages. Percentages will be calculated according to the number of patients for whom data are available. Continuous variables will be summarised using mean and SD, and median and interquartile range (IRQ, Q1-Q3). Baseline measures will include all socio-demographic, clinical and medical information, collected at baseline; some of these data will be defined after the results of investigations have been completed (e.g. final pathological diagnosis) or central adjudication of the brain and vascular imaging (e.g. site and degree of LVO, and grading of collateral vessel status).

### **3.5 Process measures of background management and treatment**

All assessments performed and interventions received between Day 1 and Day 7 will be described by intervention group. No formal statistical tests are planned for these variables.

Protocol deviations will be categorised and reported as the number and proportion of subjects experiencing a deviation. A listing of all protocol deviations will be provided.

### **3.6 BP management**

BP measurements collected during the first 24 hours will be summarised using descriptive and longitudinal mean plots. The overall mean per treatment arm, and overall difference (and 95% confidence interval [CI]) between treatment arms, will be calculated using a repeated-measure linear mixed model with a fixed effect of treatment, a fixed categorical effect of time, a fixed interaction between treatment and time, and a repeated patient effect (to model within-patient correlations assuming a compound-symmetry structure). We will adjust for stratification variables by including a random site effect, a fixed effect for time from onset to recanalisation (<6 vs ≥ 6 hours), and a fixed effect for baseline NIHSS (<17 vs ≥ 17). Estimates will be weighted to reflect the unequal spacing between measurements.

BP lowering medications administered during the first 24 hours, and during days 2-7, will be described as the number and proportion of participants receiving each medication. This will include method of intravenous (iv) administration as well as the number of different iv or oral medications (0, 1, 2, ≥3) taken. No statistical test will be performed.

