10.2 Statistical Analyses

The intention to treat (ITT) principle will be applied in analyzes. Baseline characteristics will be summarised by treatment group. The primary end-point will be analyzed by means of an ordinal logistic regression with adjustment for stratification variables. Sensitivity analyses including additional covariate adjustments and different assumptions about the missing data mechanism will be conducted to assess the robustness of the results. Continuous endpoints, such as blood pressure will be analysed using a repeated-measure linear mixed model adjusted for the stratification factors. The number of patients reporting any SAE, the occurrence of specific SAEs, and discontinuation due to SAEs, will be tabulated using MedDRA terminology.

Heterogeneity of treatment on the primary endpoint and sICH will be assessed in subgroups: age (<65 vs ≥65 years), onset time to recanalization (<6 vs ≥6 hours), systolic and diastolic BP (above vs below median), ethnicity, presumed etiological AIS subtype, NIHSS at baseline (above vs below median), ASPECT score (<6 vs ≥6) in the intensive BP lowering group, whether the patients enrolled after 6 hours meet DEFUSE 3 perfusion imaging criteria late window thrombectomy (ASPECT score and perfusion imaging criteria will be assessed by RAPID software, which will be installed at the sites by iSchemaView, Inc.).

Details of all analyses will be specified a priori in a full Statistical Analysis Plan (SAP).

We anticipate conducting 2 interim efficacy analyses when 30% and 60% of the 90-day data are available and using Haybittle-Peto stopping boundaries. The α -level for the final analysis will be the conventional significance level ($\alpha = 0.0482$).

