### **3.8.4 Imaging endpoints**

Infarct and oedema size will be analysed using linear mixed models with the same fixed and random effects as the main outcome analysis. Given that baseline measurements may not be available for all patients, we will use a constrained longitudinal data analysis (cLDA) model with both the baseline value and the follow-up value included as outcomes. The cLDA model constraints the mean baseline values to be equal between the two arms, which is a plausible assumption in a randomised trial. This approach has the advantage that any patient with at least one measurement (baseline or follow-up) can be included in the analysis instead of discarding patients with a missing baseline measurement. The effect of the intervention will be estimated as the mean difference and 95%CI at the follow-up time.

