Eyes Open	xxx	xxx	xxx
1=none	xxx xx.x%	xxx xx.x%	xxx xx.x%
2=To pain	xxx xx.x%	xxx xx.x%	xxx xx.x%
3=To speech	xxx xx.x%	xxx xx.x%	xxx xx.x%
4=Spontaneously	xxx xx.x%	xxx xx.x%	xxx xx.x%
Verbal Response	xxx	xxx	xxx
1=none	xxx xx.x%	xxx xx.x%	xxx xx.x%
2=Incomprehensible sounds	xxx xx.x%	xxx xx.x%	xxx xx.x%
3=Inappropriate words	xxx xx.x%	xxx xx.x%	xxx xx.x%
4=Confused	xxx xx.x%	xxx xx.x%	xxx xx.x%
5=Orientated	xxx xx.x%	xxx xx.x%	xxx xx.x%
Motor Response	xxx	xxx	xxx

	Intensive BP lowering (N = )	Guideline-recommended BP lowering (N = )	Total (N = )
1=none	xxx xx.x%	xxx xx.x%	xxx xx.x%
2=Extension to pain	xxx xx.x%	xxx xx.x%	xxx xx.x%
3=Flexion to pain	xxx xx.x%	xxx xx.x%	xxx xx.x%
4-Withdraws	xxx xx.x%	xxx xx.x%	xxx xx.x%
5=Localises to pain	xxx xx.x%	xxx xx.x%	xxx xx.x%
6=Obey commands	xxx xx.x%	xxx xx.x%	xxx xx.x%
Time from onset to diagnostic CT	xxx	xxx	xxx
Mean (SD)	xxx.x (xxx.x)	xxx.x (xxx.x)	xxx.x (xxx.x)
Median (Q1; Q3)	xxx (xxx; xxx)	xxx (xxx; xxx)	xxx (xxx; xxx)
min max	xxx to xxx	xxx to xxx	xxx to xxx
Time from onset to diagnostic MRI	xxx	xxx	xxx
Mean (SD)	xxx.x (xxx.x)	xxx.x (xxx.x)	xxx.x (xxx.x)
Median (Q1; Q3)	xxx (xxx; xxx)	xxx (xxx; xxx)	xxx (xxx; xxx)
min max	xxx to xxx	xxx to xxx	xxx to xxx
Time from onset to groin puncture	xxx	xxx	xxx
Mean (SD)	xxx.x (xxx.x)	xxx.x (xxx.x)	xxx.x (xxx.x)
Median (Q1; Q3)	xxx (xxx; xxx)	xxx (xxx; xxx)	xxx (xxx; xxx)
min max	xxx to xxx	xxx to xxx	xxx to xxx
Time from groin puncture to recanalisation	xxx	xxx	xxx
Mean (SD)	xxx.x (xxx.x)	xxx.x (xxx.x)	xxx.x (xxx.x)
Median (Q1; Q3)	xxx (xxx; xxx)	xxx (xxx; xxx)	xxx (xxx; xxx)
min max	xxx to xxx	xxx to xxx	xxx to xxx
Time from recanalisation to randomisation	xxx	xxx	xxx
Mean (SD)	xxx.x (xxx.x)	xxx.x (xxx.x)	xxx.x (xxx.x)
Median (Q1; Q3)	xxx (xxx; xxx)	xxx (xxx; xxx)	xxx (xxx; xxx)
min max	xxx to xxx	xxx to xxx	xxx to xxx
Time from onset to randomisation	xxx	xxx	xxx
Mean (SD)	xxx.x (xxx.x)	xxx.x (xxx.x)	xxx.x (xxx.x)
Median (Q1; Q3)	xxx (xxx; xxx)	xxx (xxx; xxx)	xxx (xxx; xxx)
min max	xxx to xxx	xxx to xxx	xxx to xxx

	Intensive BP lowering (N = )	Guideline-recommended BP lowering (N = )	Total (N = )
Systolic blood pressure after recanalisation	xxx	xxx	xxx
Mean (SD)	xxx.x (xxx.x)	xxx.x (xxx.x)	xxx.x (xxx.x)
Median (Q1; Q3)	xxx (xxx; xxx)	xxx (xxx; xxx)	xxx (xxx; xxx)
min max	xxx to xxx	xxx to xxx	xxx to xxx
Diastolic blood pressure after recanalisation	xxx	xxx	xxx

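### The 24-hour blood pressure model in SAP 3.6 leaves out the pre-treatment reading that the trial already records, and so gives up a small gain in precision that needs no new data

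*SAP*

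**What the plan says.** SAP 3.6 gives the model in full. Its structure is "a fixed effect of treatment, a fixed categorical effect of time, a fixed interaction between treatment and time, and a repeated patient effect" with compound symmetry. The covariates follow: "We will adjust for stratification variables by including a random site effect, a fixed effect for time from onset to recanalisation" (under 6 hours against 6 or more) "and a fixed effect for baseline NIHSS" (under 17 against 17 or more). The estimates are then weighted for the uneven spacing of the readings. Protocol 10.2 sets the same covariates: "Continuous endpoints, such as blood pressure will be analysed using a repeated-measure linear mixed model adjusted for the stratification factors".

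The response is described only in general terms: "BP measurements collected during the first 24 hours will be summarised using descriptive and longitudinal mean plots". Section 3.6 does not say whether the reading at randomisation is one of the modelled time points.

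Pre-treatment BP is recorded. Eligibility requires "Sustained SBP ≥140 mmHg (defined as 2 successive readings <10 mins apart) within 3 hours after recanalisation". The protocol's schedule of evaluations (Table 2) asks for two BP readings at baseline. SAP Table 1 has the row "Systolic blood pressure after recanalisation" with a matching diastolic row, and SAP Table 8 starts both the systolic and the diastolic series at randomisation.

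For infarct and oedema size the SAP does bring the baseline value into the model (3.8.4): "The cLDA model constraints the mean baseline values to be equal between the two arms".

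**The concern.** In a repeated-measures comparison, the pre-treatment value of the outcome is usually the first covariate to consider, and here it is the one left out. The overall BP difference, with its interval and p-value, is printed on SAP Figure 2. It is the trial's summary evidence that the two strategies separated, and it will colour how any mRS result is read.

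Two things are given up. The interval is somewhat wider than the data allow, and any chance difference in randomisation BP stays in the reported estimate. There is also a small gap in specification: two programmers could follow 3.6, one with the randomisation reading in the response and one without, and report slightly different differences.

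**Working it through.** **The plan's own figure.** The documents give no SD, standard error or power for the BP contrast, so there is nothing of that kind to reproduce. The one figure used here is the total of 2257, which is set for the mRS outcome. Whitehead's formula with OR 0.77, two-sided alpha 0.0482, 90% power and the stated control distribution gives

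N = 12 × (1.9756 + 1.2816)² / [(ln 0.77)² × (1 − Σp̄³)] = 127.3 / (0.06831 × 0.9743) ≈ 1913.

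Allowing for losses, 1913 / 0.95³ = 2231 and 1913 / (0.95 × 0.90) = 2237. Both are within about 1% of 2257, so the total can be taken as it stands.

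**Inputs for the BP contrast.** N = 2257, allocated 1:1 (protocol 6.1). Assumed, because the documents do not give them: the SD of a patient's 24-hour mean systolic BP (10, 15 or 20 mmHg) and its within-arm correlation ρ with the pre-treatment reading (0.2, 0.3 or 0.5).

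**Formula.** SE of the difference = (2 × SD / √N) × √(1 − ρ²), with ρ set to 0 when there is no adjustment. The 95% half-width is 1.96 × SE. For SD 15 without adjustment: 30 / √2257 = 0.63 mmHg, and 1.96 × 0.6315 = 1.24 mmHg.

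| | Unadjusted | ρ = 0.2 | ρ = 0.3 | ρ = 0.5 |
|---|---|---|---|---|
| √(1 − ρ²) | 1 | 0.980 | 0.954 | 0.866 |
| Interval narrower by | – | 2% | 5% | 13% |
| Half-width, SD 10 (mmHg) | 0.83 | 0.81 | 0.79 | 0.71 |
| Half-width, SD 15 (mmHg) | 1.24 | 1.21 | 1.18 | 1.07 |
| Half-width, SD 20 (mmHg) | 1.65 | 1.62 | 1.57 | 1.43 |

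**Bias.** In 2,000 simulated trials per correlation (1,072 patients per arm, SD 15, true difference −20 mmHg), the mean estimate lay between −19.99 and −20.01 mmHg with and without the covariate. Only the spread differed: at ρ = 0.5 the empirical SE was 0.64 unadjusted and 0.55 adjusted.

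**Chance imbalance.** One SE of baseline imbalance is 2 × SD_base / √N, and the slope that carries it into the outcome is ρ × SD / SD_base. Their product is ρ × 2 × SD / √N, so the baseline SD cancels. At SD 15 it is 0.63 × 0.2, 0.3 or 0.5 = 0.13, 0.19 or 0.32 mmHg.

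**Does detection of separation change?** The predecessor trial separated by 150 − 144 = 6 mmHg (protocol 4.2.3). Unadjusted, 6 / SE is 14.3, 9.5 and 7.1 at SD 10, 15 and 20. The difference detectable with 90% power is already 1.4, 2.0 and 2.7 mmHg. With a third of the patients (753), power for 6 mmHg is still at least 98.4%.

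**If the randomisation reading is in the response.** Treatment by time is unconstrained, so that reading would get its own treatment difference and supply no baseline adjustment. Its weight in the overall difference follows from the recording schedule in protocol 6.10.5: every 15 minutes for 1 hour, hourly to 6 hours, then 6-hourly to 24 hours. That is 12 readings, or 13 with randomisation. Under trapezoid weights (the SAP does not name its weights) it is (0.25 / 2) / 24 = 0.5%. On a 20 mmHg separation, the gap between the 120 and 140 mmHg limits, the dilution is about 0.1 mmHg. Equal weights would give 1/13 = 7.7%, but 3.6 rules these out by weighting for spacing.

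**The case against.** The case for leaving 3.6 alone is substantial. BP separation is neither a primary nor a secondary outcome (SAP 2.4), and it lies outside the multiplicity family in 3.1.1. Tables 4, 5, 7 and 8 also describe it. The model is the one that protocol 10.2 prespecifies. The size of the gain rests on assumptions. Entry is cut off at 140 mmHg and both arms are then managed to a target, both of which tend to lower the correlation, so the 0.5 column is the least likely.

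All of this stands, and it limits the size of the point. It does not supply the missing term: nothing else in either document brings pre-treatment BP into the model, and protocol 10.2 leaves the detail of analyses to the SAP.

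The comparison with 3.8.4 has limits too. That section adopts its constrained-baseline model because some baseline scans will be missing, not as a general rule for continuous outcomes. A reader might infer that 3.6 breaks the SAP's own standard. It does not; 3.8.4 shows only that a suitable model is already in the plan.

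**Conclusion.** SAP 3.6 omits a covariate that the trial already collects, and including it would be a minor improvement. The gain is an interval about 2-5% narrower at a correlation of 0.2-0.3, the more plausible range, and up to 13% narrower at 0.5. It rests on an assumed correlation and, for the figures in mmHg, an assumed SD. The adjusted estimate would also be free of a chance imbalance that would typically contribute 0.1-0.3 mmHg at SD 15.

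Three stronger readings are not supported:

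- **That the planned contrast is biased.** Randomisation makes it unbiased without the covariate, and its standard error already allows for chance imbalance.
- **That the evidence of BP separation is at risk, or that the primary analysis is affected.** A 6 mmHg difference lies 7 to 14 standard errors from zero without adjustment. The mRS analysis, its alpha and the sample size do not involve this model.
- **That a pre-treatment contrast seriously dilutes the overall difference.** The SAP does not say that the randomisation reading is modelled. If it is, spacing weights leave it about 0.5% of the total.

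The eligibility rule should not be over-read either. It guarantees two qualifying readings for systolic BP only, so the covariate should be the recorded pre-treatment value that the SAP tables report for both pressures.

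**What to change.** Amend 3.6 before unblinding:

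1. In the systolic model, include the recorded randomisation (post-recanalisation) systolic BP as a continuous covariate with a time interaction, so that its influence may fade over the 24 hours. Do the same with diastolic BP in the diastolic model. Alternatively, model that reading as a baseline constrained equal between arms, as in 3.8.4, which also handles missing baseline values.
2. Name the reading. SAP Table 1 lists BP on arrival as well as after recanalisation, and Table 8 has a randomisation row.
3. State that the pre-treatment reading does not contribute to the time-weighted overall difference.

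The cost is one covariate and its interaction in each of two models, and no new data. The covariate route needs a rule for missing baseline values. Because protocol 10.2 mentions only the stratification factors, the SAP should record the addition as a deliberate extension.
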